115	CHAPTER 12: MISCELLANEOUS CONSIDERATIONS.....	45
116	12.1 Prohibited Medications, Treatments, and Procedures	45
117	12.2 Participant Withdrawal.....	45
118	12.3 Confidentiality.....	45
119	CHAPTER 13: STATISTICAL CONSIDERATION	46
120	13.1 Statistical and Analytical Plans	46
121	13.2 Statistical Hypotheses	46
122	CHAPTER 14: DATA COLLECTION AND MONITORING	48
123	14.1 Case Report Forms and Device Data	48
124	14.2 Study Records Retention.....	48
125	14.3 Protocol Deviations	48
126	CHAPTER 15: ETHICS/PROTECTION OF HUMAN PARTICIPANTS	49
127	15.1 Ethical Standard	49
128	15.2 Institutional Review Boards	49
129	15.3 Informed Consent Process.....	49
130		

Protocol Summary

PARTICIPANT AREA	DESCRIPTION
Title	Safety of the Tandem t:slim X2 with Control-IQ Automated Insulin Delivery System in Preschoolers, age 2-6 Years Old.
Investigational Device	Tandem Control-IQ with G6 Continuous Glucose Monitor
Objectives	To assess study the safety profile of the Tandem t:slim X2 with Control-IQ system in children with T1D aged 2-6 years old under free living condition
Study Design	A single-arm, multi-center, clinical study
Number of Sites	3 independent clinical sites – sharing IDE and regulatory documentation only
Endpoint	Number of subjects with less than 6% time below 70 mg/dL and less than 40% time above 180 mg/dL.
Population	
Key Inclusion Criteria
 
 • Age ≥ 2 and < 6 years old at the time of visit 1 • Clinical diagnosis, based on investigator assessment, of type 1 diabetes for at least 3 months and using insulin at the time of enrollment • Use of an insulin pump in the past 3 months • Use of Dexcom G6 for at least 11 out of the last 14 days 
Key Exclusion Criteria
 
 • Hypoglycemia induced seizure or loss of consciousness in the past 3 months • Concurrent use of any non-insulin glucose-lowering agent • A condition, which in the opinion of the investigator or designee, would put the participant or study at risk.
Sample Size	Up to 15 participants
Participant Duration	About 14 days
Protocol Overview/Synopsis	48 hour hotel stay with 24/7 study team supervision followed by parental remote monitoring for 72 hours of at-home use

Study Visits and Procedures Schedule

	SCREENING	OPEN LOOP AT-HOME USE	PRE- ADMISSION CHECK-IN	HOTEL ADMISSION	CLOSED LOOP AT- HOME USE	POST- ADMISSION CHECK-IN
DURATION	ABOUT 3 HOURS		ABOUT 30 MINUTES	ABOUT 48 HOURS	ABOUT 72 HOURS	ABOUT 30 MINUTES

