246 at the University of Virginia, Stanford University, and the Barbara Davis Center at the University
247 of Colorado. Children and a parent/guardian(s) will use the system at home in Open Loop until the
248 start of the Hotel Admission. The child participant will then use the Control-IQ System during a
249 ~48 hours study hotel/house admission. The child participant will then use the Control-IQ System
250 at home for 72 hours under parental supervision and remote monitoring by the study team.

251 **1.5.3 Clinical Sites**

252 Each clinical site will perform the trial independently, seeking their own local IRB approval.

253 • The University of Virginia-Center for Diabetes Technology

254 • [name]

255

256 • Stanford University

257 • [name]

258

259 • Barbara Davis Center for Diabetes, University of Colorado Anschutz Medical Campus:

260 • [name]

261 **1.5.4 Study Diagram**

[figure not shown]

Figure 2: Study Diagram

265 **Chapter 2: STUDY ENROLLMENT AND SCREENING**

266 **2.1 Participant Recruitment and Enrollment**

267 Enrollment will proceed with the goal of completing 15 participants in this trial, approximately 5
268 participants per clinical site.

269 Enrollment at the University of Virginia will be defined as a parent/child dyad as the parent is
270 completing the questionnaire at the conclusion of the study.

271 Up to 25 participants may sign the consent form.

272 **2.2 Informed Consent and Authorization Procedures**

273 Consenting procedures and documentation is defined in section 15.3.

274 **2.3 Participant Inclusion Criteria**

275 Child participants must meet all of the following inclusion criteria in order to be eligible to
276 participate in the study.

- 277 1. Age \geq 2 and $<$ 6 years old at the time of consent
- 278 2. Clinical diagnosis, based on investigator assessment, of type 1 diabetes for at least 3 months
279 and using insulin at the time of enrollment
- 280 3. Use of an insulin pump in the past 3 months
- 281 4. Use of Dexcom G6 for at least 11 out of the last 14 days
- 282 5. Parent/guardian(s) have familiarity with and use of carbohydrate ratios for meal boluses
- 283 6. Living with one or more parent/guardian knowledgeable about emergency procedures for
284 severe hypoglycemia and able to contact emergency services and study staff

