1068 Participation in the study is voluntary, and a participant may withdraw at any time. For participants
1069 who withdraw, their data will be used up until the time of withdrawal.

1070 **12.3 Confidentiality**

1071 For security and confidentiality purposes, subjects will be assigned an identifier that will be used
1072 instead of their name. Protected health information gathered for this study may be shared with the
1073 third party collaborators. De-identified subject information may also be provided to collaborators
1074 involved in the study after the appropriate research agreement has been executed.

1075 **Chapter 13: STATISTICAL CONSIDERATION**

1076 **13.1 Statistical and Analytical Plans**

1077 This trial is single-armed and not powered to detect differences between groups. The study is
1078 designed to obtain a primary safety profile on patients in this age-group.

1079 This study is an early feasibility study that will test the safety of t:slim X2 with Control-IQ
1080 Technology in an outpatient setting. These studies would generate up to 75 days of closed-loop
1081 data. This sample size allows for subject withdrawal.

1082 **13.2 Statistical Hypotheses**

1083 **13.2.1 Primary Outcome**

1084 Number of subject with less than 6% time below 70mg/dL and less than 40% time above
1085 180mg/dL.

1086 **13.2.2 Secondary Outcome**

- 1087 1. % time spent <70 mg/dl, <60mg/dl, <54mg/dL, and <50mg/dL
- 1088 2. % time spent >180mg/dl, and >250mg/dl, >300 mg/dl
- 1089 3. % time spent between 70-180mg/dl
- 1090 4. % time spent between 70-150mg/dl
- 1091 5. Number of hypoglycemia below 70 mg/dL
- 1092 6. Number of carbohydrate treatments, as well as total amount of carbohydrates used for
1093 treatments.
- 1094 7. Time spent in closed loop
- 1095 8. Time with available CGM
- 1096 9. Number of subject with more than 70% time in 70-180mg/dL range with less than 4%
1097 time below 70mg/dL

1098 **13.2.3 Success Criteria / Goal**

1099 As a general rule, a session will be considered useful for data analysis if the subject completes
1100 close to 80% of the active study protocol. Sessions are considered separate: (i) Supervised
1101 Phase=complete at least 38 hours of AP; (ii) at home use=complete at least 56 hours of AP.

1102 *The primary goal will be considered met if the primary outcome is achieved for 65% or more of
1103 the subjects.*

1104 **13.2.4 Statistical Analysis Plan**

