1160 risks and possible benefits of participation will be provided. Consent forms will be IRB approved
1161 and the participant will be asked to read and review the document. The investigator or their
1162 delegate will explain the research study to the parent/guardian(s) and answer any questions that
1163 may arise. All participants will receive a verbal explanation in terms suited to their comprehension
1164 of the purposes, procedures, and potential risks of the study and of their rights as research
1165 participants. Parent/guardian(s) will have the opportunity to carefully review the written consent
1166 form and ask questions prior to signing.

1167 The parent/guardian(s) will sign the informed consent document prior to any procedures being
1168 done specifically for the study. The parent/guardian(s) may withdraw their child's consent at any
1169 time throughout the course of the trial. A copy of the informed consent document will be given to
1170 the parent/guardian(s) for their records. The rights and welfare of the participants will be protected
1171 by emphasizing to them that the quality of their medical care will not be adversely affected if they
1172 decline to participate in this study.

1173 A child participant is considered enrolled when the informed consent form has been signed.

1174 **15.3.2 Participant and Data Confidentiality**

1175 The study monitor, representatives of the IRB or device company supplying study product may
1176 inspect all documents and records required to be maintained by the investigator, including but not
1177 limited to, medical records (office, clinic, or hospital) for the participants in this study.

UNIVERSITY OF VIRGINIA

1178 The study participant's contact information will be securely stored at the clinical site for internal
1179 use during the study. At the end of the study, all records will continue to be kept in a secure
1180 location for as long a period as dictated by local IRB and Institutional regulations.

1181 Study participant research data, which is for purposes of statistical analysis and scientific reporting,
1182 will be transmitted to and stored at the University of Virginia Center for Diabetes Technology.
1183 This will not include the participant's contact or identifying information. Rather, individual
1184 participants and their research data will be identified by a unique study identification number. The

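### The plan does not say which children, or which hours of CGM data, count toward the 65% goal, and the minimum-hours rule and the withdrawal rule are not reconciled

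*Combined protocol and SAP*

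**What the plan says.** **Hours rule.** Section 13.2.3 states, as a general rule, that "a session will be considered useful for data analysis if the subject completes" close to 80% of the active protocol. It treats the two sessions separately and gives the minimums: "Phase=complete at least 38 hours of AP; (ii) at home use=complete at least 56 hours of AP".

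**Withdrawal rule.** Section 12.2 says that, for participants "who withdraw, their data will be used up until the time of withdrawal". It sets no minimum duration and does not say which analysis uses the data.

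**Goal.** Section 13.2.3 continues: "The primary goal will be considered met if the primary outcome is achieved for 65% or more of" the subjects. Section 13.2.4 compares the proportion of subjects with 65%. Neither defines an analysis set. The counts available elsewhere differ:
- Section 2.1: "Enrollment will proceed with the goal of completing 15 participants in this trial" and "Up to 25 participants may sign the consent form".
- Protocol Summary: "Up to 15 participants".
- Section 15.3.1: "A child participant is considered enrolled when the informed consent form has been signed".

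**Window.** Section 13.2.1 gives the limits (under 6% of time below 70 mg/dL and under 40% above 180 mg/dL) but no period. Section 13.2.4 assigns the entire period and the separate phases to secondary outcomes. It scores the primary outcome by phase only for the McNemar comparison.

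**Device stops.** Section 11.4.1 ends device use after one DKA episode or one severe hypoglycemia event. Section 7.2.2 ends participation for ketones above 3.0 mmol/L at home.

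**The concern.** Hours of closed-loop use are known only after treatment starts, and the protocol's own safety stops can cut them short. A usability rule built on them can therefore remove a child because of what happened on the device. In a study whose primary aim is safety, that needs an explicit decision.

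The rules also give different data for the same child. One who withdraws partway through a session keeps all data to that point under 12.2 but may lose that session under 13.2.3. Section 12.2 does not clearly cover a child whose device is stopped under 11.4.1 but who stays in the study.

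At stake is whether the one success criterion is met. If the set and window are left open, they can be chosen after the data are seen. If 13.2.3 is applied to the phase comparison, which is meant to detect loss of performance at home, children whose home use ended early have no home value in it.

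**Working it through.** **1. The plan's own figure.** Inputs from 13.2.4: effect size w = 0.64 and chi-square goodness of fit against 65%. N = 15 is from 2.1. Alpha is taken as 0.05 with 1 degree of freedom (13.2.4 states 0.05 alongside the phase comparisons). Noncentrality = N·w² = 15 × 0.64² = 6.144, giving power 69.8%. The stated 70% reproduces with all 15 children scored. With 13 scored it is 63.6%. Under the same reading, the implied responder rate is 0.65 + 0.64 × √(0.65 × 0.35) = 0.955.

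**2. Who drops out under 13.2.3 as written.**
- Stopped in the hotel before 38 h, with no home use: no useful session, so no contribution to the proportion.
- Past 38 h in the hotel, stopped at home before 56 h: still counted, but possibly scored on the hotel stay alone, and without a home value for McNemar.

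**3. Effect on the 65% goal.** The smallest count that meets it is 0.65n rounded up: 9 of 13, 10 of 14, 10 of 15. The numbers excluded are assumptions, because the documents give no stop rate.

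| All 15 counted | Excluded | Remaining | Change |
|---|---|---|---|
| 9/15 = 60.0%, not met | one failure | 9/14 = 64.3%, not met | none |
| 9/15 = 60.0%, not met | two failures | 9/13 = 69.2%, met | reversed |
| 10/15 = 66.7%, met | one success | 9/14 = 64.3%, not met | reversed |

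**4. Chance of meeting the goal.** Suppose two children fail and have no useful session, and the other 13 respond independently at rate p. With the two excluded, at least 9 of 13 must respond. With them counted, at least 10 of 13 must respond, to reach 10/15.

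| p | Two excluded: P(Bin(13, p) ≥ 9) | Two counted: P(Bin(13, p) ≥ 10) |
|---|---|---|
| 65% | 50.1% | 27.8% |
| 75% | 79.4% | 58.4% |
| 95.5% | 99.98% | 99.8% |

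**5. Effect of the window on one child.** Take a child with 48 h in the hotel who withdraws at home hour 55. Section 12.2 gives 48 + 55 = 103 h; applying 13.2.3 leaves 48 h.
- Hotel 45% and home 30% above 180 mg/dL (assumed): (48 × 45 + 55 × 30)/103 = 37.0%. The child passes on pooled data and fails on the hotel alone.
- Hotel 35% above 180 mg/dL (the normative mean in 13.2.4): pooled time reaches 40% once home time is (40 × 103 − 48 × 35)/55 = 44.4%. From there the child fails on pooled data and passes on the hotel alone.

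The window can therefore move a score either way.

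**The case against.** The best defence is that the intended reading is easy to guess. Section 13.1 expects up to 75 days of closed-loop data, which is 15 children × 5 days, and the 70% power needs 15 scored children. Both point to 15 device users over both phases. A child who consents but never starts has no closed-loop data to score, so all enrolled children is a weak candidate for the denominator. The hours rule is hedged twice and may be an ordinary data-sufficiency check, and this is an early feasibility study. All of this stands as inference. None of it is stated, and it does not settle what happens to a child who starts and stops early.

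Four stronger readings are tempting and not supported:
- *The two rules contradict each other.* They can coexist if 12.2 governs retention of data and 13.2.3 governs usable sessions. They are unreconciled.
- *The hours rule biases the trial toward success.* The direction depends on whether the excluded children are failures or successes.
- *Safety events disappear.* Adverse events are still reported and reviewed under 11.1.2 and 11.5. The gap is in the CGM responder count and the phase comparison.
- *The home ketone stop removes a child from the primary count.* It does not, once the child has 38 h in the hotel.

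**Conclusion.** The gap is real and should be fixed before the data are analysed. The plan leaves open which rule governs, who is in the denominator, and which window scores the primary outcome. A literal reading of 13.2.3 can take a child stopped early in the hotel for a safety event out of the primary safety proportion.

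The size depends on performance. In the two-failure scenario the choice shifts the chance of meeting the goal by 50.1 − 27.8 = 22.3 percentage points at a 65% responder rate, 79.4 − 58.4 = 21.0 at 75%, and less than 0.2 at 95.5%. These figures assume two such children and independent responses among the rest; they are not estimates of how often the result would change. Confidence is high that the rule is missing. The practical impact is uncertain because no stop rate is given. The stated power is not wrong, but it presumes that all 15 children are scored.

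**What to change.** In 13.2.3 and 13.2.4:
1. Define the primary set as every child in whom Control-IQ is activated at the hotel.
2. Score each child on all CGM data from activation to the end of home use, or to permanent device stop or withdrawal if earlier. Include time when Control-IQ is temporarily off.
3. State that this takes precedence over the hours rule, for device stops as well as for withdrawals under 12.2.
4. Keep the 38 h/56 h set as a labelled sensitivity analysis.
5. Add a second sensitivity count in which children stopped for DKA, severe hypoglycemia or ketones above 3.0 mmol/L are scored as not meeting the outcome.
6. In the phase comparison, report how many children lack a useful home session and why.

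The cost is analysis wording, with no new data or visits and no change to any clinical rule. Some children will be scored on a short CGM record, and the reported proportion may be slightly less favourable.

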1105 Proportions of subject matching primary criteria will be computed and directly compared to 65%
1106 (considered baseline). Further analysis will be performed using a chi² test of goodness of fit. Based
1107 on prior data in 6-12 year olds we anticipate a possible effect size of 0.64, which would allow to
1108 detect a difference with 70% power considering our sample size.

CLINICAL PROTOCOL

1109 Overall outcomes will be compared to the normative data below (values derived from the analysis
1110 of 30 6-12 year old T1D subjects using pumps and CGM and rounded for ease of use):

	Baseline	
	mean	std
% time below 50mg/dL	0.5%	0.5%
% time below 54mg/dL	1%	0.8%
% time below 60mg/dL	2%	1%
% time below 70 mg/dL	4%	2.5%
% time between 70-140mg/dL	40%	9%
% time between 70-180mg/dL	60%	9%
% time above 180mg/dL	35%	9%
% time above 250mg/dL	11%	5%
% time above 300mg/dL	4%	3%
Average CGM [mg/dL]	162.0	15.0

1111 This analysis will be performed using a single group one sided t-test for mean comparison for
1112 outcomes that can be assumed normally distributed and One-Sample Wilcoxon Signed Rank test
1113 for median comparison for the others, this analysis is not powered.

1114 Secondary outcomes will be reported for the entire period and for the supervised and home phases
1115 separately. Outcomes by phase will be compared to each other to assess possible loss of
1116 performances during the transition at home. For this purpose, McNemar's tests will be used to
1117 compare the supervised phase to the home phase for the primary outcome and secondary outcome
1118 # 6, 7, and 8. All other outcomes will be analyzed using repeated measure ANOVA. Significance
1119 of 0.05 will be used.

1120 This analysis is not powered.

1121 **Chapter 14: DATA COLLECTION AND MONITORING**

1122 **14.1 Case Report Forms and Device Data**

1123 The study data are collected through a combination of case report forms (electronic and paper) and
1124 electronic device data files obtained from the software and individual hardware components.
1125 These electronic device files and electronic CRFs are considered the primary source
1126 documentation.

1127 When data are directly collected in electronic case report forms, this will be considered the source
1128 data. Records will be maintained in accordance with ICH E6 and institutional regulatory
1129 requirements for the protection of confidentiality of participants.

1130 **14.2 Study Records Retention**

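### The 38 h/56 h session rule exempts no outcome; applied to closed-loop use (outcome 7), it truncates the quantity being estimated

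*Combined protocol and SAP*

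**What the plan says.** Section 13.2.3 (Success Criteria / Goal) sets the inclusion rule. It opens with "As a general rule, a session will be considered useful for data analysis if the subject completes" and continues "close to 80% of the active study protocol". It then treats the two phases as separate sessions and gives the minimum for each: "Phase=complete at least 38 hours of AP; (ii) at home use=complete at least 56 hours of AP". It does not say which outcomes the rule governs, and it exempts none.

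Section 13.2.2 lists nine secondary outcomes. Number 7 is "Time spent in closed loop" and number 8 is "Time with available CGM". Neither has a unit, a denominator or an analysis set.

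Section 13.2.4 states "Secondary outcomes will be reported for the entire period and for the supervised and home phases" separately. It then uses a paired test to "compare the supervised phase to the home phase for the primary outcome and secondary outcome" numbers 6, 7 and 8, in order to see whether performance is lost in the move to home. It declares this analysis not powered.

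Section 12.2 says that data from participants who withdraw are used up to the time of withdrawal.

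The Protocol Summary gives the nominal phase lengths: "48 hour hotel stay with 24/7 study team supervision followed by parental remote monitoring for 72 hours of at-home use".

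**The concern.** An inclusion rule based on exposure can be reasonable for a glycaemic outcome, where a session with little closed-loop time says little about the algorithm. It does not suit an outcome that measures exposure. For outcome 7 the variable that decides whether a session is analysed is the variable being summarised, so the rule removes low values and keeps high ones.

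The low values are the informative ones. The protocol expects closed loop to lapse. Section 4.1.1 provides for open-loop operation during disconnections and technical difficulties, and for Control-IQ to be off for about four hours after insulin given by another route. Sections 7.2.2 and 11.4.1 list events that end device use. Section 11.2 keeps component disconnections, and communication failures that do not lead to system replacement, off the Device Issue Form. Outcomes 7 and 8 are therefore a main place where such problems would be visible.

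The phase comparison has the same difficulty. It is paired, so a child whose home session falls below 56 h contributes no pair. A drop in use at home, if large enough, removes itself from the analysis designed to find it.

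**Working it through.** **Inputs.** Thresholds of 38 h and 56 h of AP (13.2.3); nominal phases of 48 h and 72 h (Protocol Summary); arrival at about 3-5 pm on day 1 (5.4); discharge after a lunch at about 11:30-12:30 on day 3 (5.6); up to 15 participants (Protocol Summary).

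**1. The plan's own figure.** 80% of 48 h is 38.4 h, and 80% of 72 h is 57.6 h. The thresholds of 38 h and 56 h are 79.2% and 77.8% of nominal time, consistent with the plan's approximate 80%.

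**2. Is the filter variable the outcome?** Section 1.2 uses closed-loop control and artificial pancreas (AP) as two names for the same system, and 5.5 refers to the time during which the AP system is active. On that usage, hours of AP are hours in closed loop, which is outcome 7.

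**3. Floors if the rule is applied to outcome 7.**
- Hotel: 38/48 = 79.2% of nominal time.
- Home: 56/72 = 77.8%.
- Whole period, both sessions qualifying: 94/120 = 78.3%.

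**4. Hotel floor on the protocol's timetable.** From 5 pm on day 1 to 11:30 am on day 3 is 42.5 h; from 3 pm to 12:30 pm is 45.5 h. Then 38/45.5 = 84% and 38/42.5 = 89%. Measured against the scheduled stay, the hotel floor is tighter than the nominal one.

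**5. Size of the bias (assumed inputs).** The documents give no distribution of closed-loop use. Taking home use as beta-distributed and cutting at 56/72:

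| Assumed mean (SD) | Sessions dropped | Mean after the rule | Overstatement |
|---|---|---|---|
| 90% (8%) | 8.5% | 91.7% | 1.7 points |
| 85% (12%) | 23.4% | 90.4% | 5.4 points |
| 80% (15%) | 36.9% | 89.45% | 9.45 points |

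A discrete example on 15 children, also assumed: with 12 at 95% and 3 at 50%, the mean over all sessions is (12×95 + 3×50)/15 = 86%, and the mean after the rule is 95%. With 14 at 95% and 1 at 30%, the figures are (14×95 + 30)/15 = 90.7% and 95%.

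**6. Effect on the phase comparison (assumed).** Take hotel use with mean 93% (SD 5%) and home use with mean 80% (SD 15%). The true drop is 13 points. After each phase is cut at its own threshold the means are about 93.3% and 89.5%, an apparent drop of about 4 points. This filters each phase separately; the documents give no within-child correlation from which to model the pairing.

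**7. Outcome 8.** The rule has no CGM-availability criterion. Any effect on outcome 8 depends on closed loop needing a CGM signal, which is plausible but is not stated as a rule. No numerical floor follows for outcome 8 from the text alone.

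**The case against.** The case against has several parts.

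- **The rule is hedged.** It is a general rule with an approximate percentage, and no analysis set is fixed for outcomes 7 and 8. A reader might infer that reported use must come out at 78% or more whatever happens in the trial. The documents do not support that: the team could analyse all sessions without contradicting the wording. The hedge does, however, leave exclusion to judgement after the data are seen.
- **Section 12.2 keeps data up to withdrawal.** This points against discarding short sessions, and it conflicts with a strict filter. It does not help with a child who stays in the study with low use, because that child has not withdrawn.
- **Hours of AP could mean elapsed hours in the AP phase.** On that reading a child with repeated drop-outs stays in and lowers outcome 7. The reading cannot be excluded, but the protocol's use of AP elsewhere favours algorithm-active hours. Truncation is exact only on the latter.
- **Outcome 8 is not the selection variable.** This stands. A reader might treat the two outcomes as equally truncated; the text does not support that.
- **The bias may be small.** This stands too. If use is uniformly high, it is under 2 points.
- **These are secondary outcomes in a small study whose primary aim is the safety profile, and the phase comparison is declared not powered.** True, and it limits the weight of the point. Lack of power does not excuse a systematic bias, though, and the plan calls the trial an early feasibility study, where sustained closed-loop use is of direct interest.

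**Conclusion.** The concern holds in conditional form. If the 38 h/56 h rule is applied to outcome 7, with AP hours read as hours in closed loop, reported use is truncated at about 79% (hotel) and 78% (home) of nominal time, or about 84-89% of the hotel stay on the timetable. The hotel-home comparison then loses the home sessions most relevant to its purpose. This goes beyond a missing detail, because a stated rule followed as written biases the estimate.

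The magnitude cannot be fixed from the documents. Under the assumed spreads the overstatement of mean use runs from about 2 to about 9 points. Outcome 8 is affected only indirectly. The plan does not make a favourable result certain; it makes one likely to be overstated and leaves the choice of sessions open. The change should be made, in proportion to a secondary outcome.

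**What to change.** - State in 13.2.3 that the 38 h/56 h rule does not apply to outcomes 7 and 8.
- Report both outcomes for every child who starts Control-IQ in the phase, as a percentage of a stated denominator. One option is the hours from Control-IQ start to the scheduled end of the phase, with early stops also listed separately with their reasons. Whether hours after a stop count as zero is a choice of estimand and should be stated; it mixes device performance with mandated or voluntary stops, which is why the separate list is useful.
- Report the number of sessions below 38 h or 56 h in each phase as a result in its own right.
- Define hours of AP, and reconcile 13.2.3 with 12.2 so that it is clear what happens to data from short sessions.

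The cost is a few sentences. The electronic device files described in 14.1 are already collected, so no new data are needed. The downside is that the reported use figure may be lower.

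### 65% is both the pass mark and the test's baseline: with 15 children the goal is met from 10/15, which alone is no evidence of a rate above 65%

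*Combined protocol and SAP*

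**What the plan says.** The primary outcome (13.2.1) counts children with less than 6% of time below 70 mg/dL and less than 40% of time above 180 mg/dL. Three statements govern how that count is judged.

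- **Pass rule (13.2.3):** "The primary goal will be considered met if the primary outcome is achieved for 65% or more of" the subjects. This is a rule on the observed proportion alone.
- **Comparison and test (13.2.4):** "Proportions of subject matching primary criteria will be computed and directly compared to 65" percent, a value the plan labels as baseline. A chi-square goodness-of-fit test then follows as further analysis.
- **Power (13.2.4):** "on prior data in 6-12 year olds we anticipate a possible effect size of 0.64, which would allow to" "detect a difference with 70% power considering our sample size". The type of effect size and the true rate behind it are not given.

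A significance level appears once, at the end of the paragraph comparing the supervised and home phases ("of 0.05 will be used"). Nothing says whether it governs the primary test or whether that test is directional. No confidence interval is planned for the primary proportion.

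On purpose, 13.1 describes an early feasibility study "designed to obtain a primary safety profile on patients in this age-group", while 1.5.1 speaks of demonstrating safety and efficacy. Section 2.1 aims for 15 completed participants.

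**The concern.** When one value is both the pass mark and the reference of the test, the goal can be met by a result that the test cannot distinguish from that reference. The plan does not say what may be concluded in that case.

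The gap matters because of how the result may be reported. Chapter 13 attaches a power figure to the comparison with 65%, and 1.5.1 sets a demonstrative purpose. A report that the primary goal was met could then be taken as a shown result even when the data are compatible with a rate at or well below 65%. The power statement adds to this: without a named effect size, a reader cannot tell which true rate the trial was sized to detect.

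**Working it through.** **Inputs.** Pass mark and reference rate p0 = 0.65 (13.2.3, 13.2.4); effect size 0.64 and power 70% (13.2.4); n = 15 (2.1). Two-sided alpha 0.05 is inferred and checked first.

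**1. Reproducing the 70%.** For a goodness-of-fit test with 1 degree of freedom and Cohen's w = 0.64, the noncentrality is n·w² = 15 × 0.4096 = 6.144. Against the critical value 3.841 (alpha 0.05) the power is 69.8%, which matches. Alpha 0.10, equivalent to a one-sided 0.05 test, gives 79.8%; alpha 0.025 gives 59.4%. Two-sided 0.05 is thus the reading that fits.

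Reading 0.64 as Cohen's h gives Φ(0.64·√15 − 1.96) = Φ(0.519) = 69.8% as well. The stated power therefore settles alpha but not the effect-size measure.

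**2. Where the goal is met.** 0.65 × 15 = 9.75, so 10/15 (66.7%) passes and 9/15 (60%) fails. Binomial P(X ≥ 10):

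| True rate | 50% | 60% | 65% | 80% | 90% |
|---|---|---|---|---|---|
| Goal met | 15% | 40% | 56% | 94% | 99.8% |

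**3. Where the test rejects.** Expected counts are 9.75 and 5.25, so χ² = (x − 9.75)² × (1/9.75 + 1/5.25) = (x − 9.75)² × 0.293.

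| Successes | χ² | Two-sided p | Exact 95% CI (Clopper-Pearson) |
|---|---|---|---|
| 10/15 | 0.018 | 0.892 | 38% to 88% |
| 11/15 | 0.458 | 0.499 | 45% to 92% |
| 12/15 | 1.484 | 0.223 | 52% to 96% |
| 13/15 | 3.095 | 0.079 | 60% to 98% |
| 14/15 | 5.293 | 0.021 | 68% to 99.8% |

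The first upward rejection is at 14/15, so at 10 to 13 the goal is met and the test is not significant. If a directional 0.05 test is meant and the p-value is halved, 13/15 becomes significant (0.039) and the range is 10 to 12. An exact one-sided binomial test gives 0.062 at 13/15, which again leaves 10 to 13.

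**4. Exact power of the 14/15 threshold.** P(X ≥ 14) = 15·p¹⁴(1 − p) + p¹⁵.

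- If 0.64 is Cohen's w: p1 = 0.65 + 0.64 × √(0.65 × 0.35) = 0.955, and exact power is 86%.
- If 0.64 is Cohen's h: p1 = sin²[(2·arcsin√0.65 + 0.64)/2] = 0.905, and exact power is 58%.

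At p = 0.65 the same expression gives 1.4%, the exact chance of an upward rejection when the true rate equals the baseline. Neither exact power is 70%, because with 15 children the test moves in whole counts.

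**The case against.** The best defence is that nothing in the plan is broken. The pass rule is complete as written, the chi-square test is labelled as further analysis, and the goal does not formally depend on it. Section 13.1 presents the trial as early feasibility, and no passage states that a met goal supports a rate above 65%. All of this stands. So does the point that the rule behaves well when the device works well: it is passed 94% of the time at a true rate of 80% and 99.8% at 90%.

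It is also fair that a test should seldom reject when its null is true, so the 56% pass probability at 65% is simply how a descriptive benchmark set at the null behaves.

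The range 10 to 13 rests on an inferred two-sided alpha. The t-test for the normative comparison in the same section is one-sided, so a directional primary test is not excluded, although it does not reproduce the 70%. On that reading the range narrows to 10 to 12 and the gap remains.

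The defence does not answer why a powered test is attached to 65% with no statement of how its result limits what a met goal means.

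**Conclusion.** The point holds as a gap in interpretation, of minor to moderate weight. With 15 analysed and a two-sided 0.05 test, any result from 10 to 13 successes meets the goal without evidence of a rate above 65%. A met goal alone therefore cannot support the purpose stated in 1.5.1. The 70% power is an asymptotic figure; exact power is 86% or 58%, depending on an effect-size measure that the plan does not name.

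Four stronger readings are tempting, and the documents do not support them:

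- **That 13.2.3 and 13.2.4 contradict each other.** They do not; one sets a benchmark and the other adds a test.
- **That 56% is a breached type I error.** The plan promises no error rate for the pass rule.
- **That a non-significant result shows the rate is no higher than 65%.** It only fails to show that it is higher.
- **That the 70% is miscalculated.** It reproduces under the usual approximation.

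The figures assume 15 analysed. Section 13.1 says the sample size allows for withdrawal, so the thresholds and the power should be restated for the number actually analysed.

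**What to change.** In 13.2.3, label the 65% rule a descriptive feasibility benchmark. State that it is passed 56% of the time at a true rate of 65% with 15 analysed, and that a rate above 65% will be claimed only if the 13.2.4 test rejects upward.

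In 13.2.4:

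- State alpha and sidedness for the primary test.
- Report the proportion with an exact (Clopper-Pearson) 95% interval.
- Preferably replace the asymptotic chi-square with an exact binomial test. The two-sided minimum-likelihood version also first rejects upward at 14/15 (p = 0.027, against 0.104 at 13/15).
- Have the sponsor say which effect-size measure and true rate lie behind 0.64, and replace 70% with the exact power at that rate for the number analysed. The documents do not settle whether w or h was used, so the value should come from the sponsor.

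The cost is wording and one restated power figure, with no extra participants. The downside is a more modest claim if 10 to 13 of 15 succeed.
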